2.1 Objectives

This is a single-center, prospective study enrolling 10 PAH patients. All eligible participants will be given carnitine supplements for 2 weeks.

2.2 Specific Aims

Primary Aim:

1. The primary objective of this study is to evaluate the effect of standard L-carnitine supplementation in PAH patients on plasma carnitine levels.

Secondary Aims:

- 1. to measure the oral consumption of carnitine in human PAH
- 2. to measure the stability over time in plasma carnitine levels in PAH patients

3 Screening and Subject Selection

3.1 Recruitment of Study Sample

Patients will be recruited from the Center for Pulmonary Vascular Disease (CPVD) at Vanderbilt University Medical Center (Nashville, TN). Potentially eligible subjects will be pre-screened by study personnel through medical record review and informed about that study to determine if they have an interest in enrolling. After the initial conversation by telephone, the subject will be provided informed consent and a link to the e-consent will be emailed directly to them. Informed consent will occur before any study procedures are performed.

3.2 Inclusion/Exclusion Criteria

Inclusion criteria:

- Adults aged 18 or older.
- Diagnosed with idiopathic, heritable, simple congenital heart defect, or drug- or toxin-associated pulmonary arterial hypertension (PAH) according to World Health Organization consensus recommendations.
- Stable PAH-specific medication regimen for three months prior to enrollment. Subjects with only a single diuretic adjustment in the prior three months will be included. Adjustments in IV prostacyclin for side effect management are allowed.
- FEV1> or = 60% predicted and no more than mild abnormalities on lung imaging

- WHO Functional Class II-IV
- Ambulatory

Exclusion criteria:

- Prohibited from normal activity due to wheelchair bound status, bed bound status, reliance on a cane/walker, activity-limiting angina, activity-limiting osteoarthritis, or other condition that limits activity
- Pregnancy
- Diagnosis of PAH etiology other than idiopathic, heritable, simple congenital heart defect, or associated with drugs or toxins
- Drug and toxin associated PAH patients with active drug use
- Prior diagnosis of cirrhosis
- Malignancy
- eGFR by MDRD <60mL/min
- Known allergy to I-carnitine supplements

3.3 Supplement Dosing

A 14-19-day supply of Carnitine supplements will be provided to the subject at Visit 2. The VUMC Pharmacy for Research will supply Nature's Bounty L-Carnitine 500mg caplets to be taken by mouth. For subjects weighing <90kg, I- carnitine will be taken at 1.5g twice a day. For subjects weighing >90kg, I-carnitine will be taken at 50 mg/kg/day split between 2 doses. Dosing for these participants will be rounded to the next whole pill to achieve approximately 50 mg/kg per day. Dosing will be incrementally titrated by 25- 50% in the event of intolerance and/or side effects limiting subject's compliance to prescribed regimen.

4 Data Collection

4.1 Consent

Written consent or e-consent will be obtained for enrollment from participants. For each consent process, study personnel will discuss the details of the study, the risks and benefits, and the subject's rights and responsibilities if they choose to participate in the trial and their right to refuse to participate. It will be made clear that their clinical care will not be affected by their decision. Written consent or e-consent will be obtained before Visit 1.

For e-consent, the patient consent process will be conducted using a REDCap-based electronic consent form. The consent form has been developed in REDCap, a secure, web-based, HIPAA-compliant, data collection platform with a user management system allowing project owners to grant and control varying levels of access to data collection instruments and data (e.g. read only, de-identified-only data views) for other users. Potential participants will participate in the consent process by either:

- 1.) Being approached in-person at a Vanderbilt Clinic and accessing the REDCap survey via iPad or other portable electronic device and/or
- 2.) Self-initiated access of consent forms on personal portable electronic devices using posted QR codes or web-links on study posters, brochures, or websites. Self-initiated accessing of consent forms may occur in clinic or at home.

During the in-person consent process, patients will be consented by a member of the key study personnel.

For self-initiated consent, contact information will be provided (email and phone) for prospective patients to contact a member of the key study personnel with questions, prior to consent.

Patient signatures will be obtained using a typed signature. Upon completion of the consent, patients will be provided with a copy of their version of the consent document by printing a pdf copy of the consent form in clinic or at their Visit 1 visit.

4.2 Study Visits and Contacts

This study will consist of four visits: Visit 1 (0 week), Visit 2 (Week 12), Visit 3 (Week 12+1 day) and Visit 4 (Week 14). The Visit 1 and Visit 3 are both estimated to take approximately 2 hours each. Visit 2 and Visit 4 are both estimated to take approximately 4 hours each. Patients will be consented by the PI, a clinical research coordinator, or a research nurse. Patient's written consent and study procedures will take place at the Pulmonary Vascular Disease Clinic (CPVD), the Clinical Research Center (CRC), there will be no changes to a patient's medication regimen.

4.2.1 Pre-visit Consent Telephone Contact (minimum -4 days)

Prior to subject's first CRC visit, the subject will consent by REDCap e-consent process and complete a 3-day ASA24 food and supplement diary.

4.2.2 Visit 1 Visit (0 Weeks)

This visit will last approximately 2 hours and occur at the Clinical Research Center at VUMC. At Visit 1, written consent will be obtained from subjects after all questions are adequately answered. The following procedures will be performed:

- written informed consent
- review inclusion/exclusion criteria
- review of medical history
- demographic data
- review of current medications
- orientation to food and supplement diary (ASA24)
- WHO functional class
- blood collection
- symptom assessment
- vital signs
- physical exam
- six-minute walk test

After fasting research labs have been drawn, the subject will have the opportunity to eat a snack. The investigator or research nurse will take a medical history, perform a physical examination including checking vital signs, and review current medications. The subject will perform the six-minute walk test.

4.2.3 Telephone Contact (Week 11)

The research coordinator will call the subject 1 week prior to Visit 2 to remind them to complete the 3-day ASA24 food and supplement diary. Study compliance will be assessed and reinforced.

4.2.4 Study Day – Visit 2 (Week 12)

All tests done at the Visit 1 visit will be repeated at the Visit 2 Visit. The following procedures will be performed:

- review of interim medical history
- review of current medications
- WHO functional class
- blood collection
- urine pregnancy test (as necessary)
- symptom assessment
- vital signs
- physical exam
- review of food and supplement diary (ASA24)
- six-minute walk test
- transthoracic echocardiography
- Dosing of Carnitine supplement

After fasting research labs have been drawn, the subject will have the opportunity to eat a snack. The investigator or research nurse will take an interim medical history, perform a physical examination including checking vital signs, and review current medications. The subject will perform the six-minute walk test. An experienced research sonographer will perform the transthoracic echocardiography.

4.2.5 Study Day- Visit 3 (Week 12+1 day)

The day following Visit 2, a brief visit will be performed with the following procedures:

- blood collection
- symptom assessment
- vital signs
- review of food and supplement diary (ASA24)
- 2 weeks supply of carnitine supplement provided

4.2.6 Telephone Contact (Week 13)

The research coordinator will call the subject a week after beginning the carnitine supplement to review and record symptoms, potential side effects, and changes in medications. Study compliance will also be assessed and reinforced.

4.2.7 Study Day- Visit 4 (Week 14)

All tests done at the Visit 2 visit will be repeated at the Visit 4 Visit. The following procedures will be performed:

- review of interim medical history
- review of current medications
- WHO functional class
- blood collection

- symptom assessment
- vital signs
- physical exam
- review of food and supplement diary (ASA24)
- six-minute walk test
- transthoracic echocardiography
- pill count of carnitine supplement

After fasting research labs have been drawn, the subject will have the opportunity to eat a snack. The investigator or research nurse will take an interim medical history, perform a physical examination including checking vital signs, and review current medications. The subject will perform the six-minute walk test. An experienced research sonographer will perform the transthoracic echocardiography.

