- Difference in plasma acylcarnitine profile from Visit 3 to Visit 4.
- Difference in lipid metabolites from Visit 3 to Visit 4.
- Correlation of change in plasma carnitine with change in Functional class.
- Correlation of change in plasma carnitine with change in six-minute walk distance.
- Correlation of change in plasma carnitine with change in BNP.
- Correlation of change in plasma carnitine concentration with TMAO concentration
- Correlation of change in plasma carnitine with change in markers of RV function including TAPSE and RV fractional area change.
- Markers of tolerability including presence of side effects, adverse events and serious adverse events.
- Pill counts at Visit 4 for adherence.

STUDY OBSERVATIONS:

- Subjects will be evaluated in person at Visit 1, Visit 2, Visit 3, and Visit 4.
- BNP, carnitine assay, lipid metabolites, carnitine, acylcarnitine, and other biomarkers will be assessed at Visit 1, Visit 2, Visit 3, and Visit 4.
- Subjects will have six-minute walk testing at Visit 1, Visit 2, and Visit 4.
- Subjects will have a transthoracic echocardiogram at Visit 2 and Visit 4.
- Subjects will submit food and supplement diary at Visit 1, Visit 2, and Visit 4.

SAMPLE SIZE AND POWER:

In a study of 28 PAH patients⁶ the mean \pm SD of plasma carnitine data was 38.6±11.1 uM. The data appeared to be normally distributed. In a pilot study²¹, L-carnitine supplementation increased free plasma carnitine concentration by 22% (Table 3 in²¹). A sample size of 10 will have 80% power to detect a within subject change in means of 8.5 (increase from Visit 1 mean of 38.6 to 47.1 after 2 weeks of treatment, representing a 22% increase) using a paired t-test with a 5% two-sided significance level. The standard deviation of within-subject differences is assumed to be 8.6 and it is calculated using SD of 11.1 assuming a moderate within-subject correlation 0.7. We plan to study 10 PAH patients in this proof-of-concept study. The study has 80% power to detect a within-subject change of effect size 1, i.e. change measured as 1 times of the SD.

DATA ANALYSIS:

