5.1 Assessments of Efficacy

Primary Endpoint: Difference in plasma carnitine concentration from Visit 1 to Visit 4.

Secondary Endpoints:

- Quantify the prevalence of carnitine supplement use
- Measure oral ingestion of carnitine in PAH patients.
- Difference in six-minute walk test from Visit 1 to Visit 2.
- Difference in functional class from Visit 1 to Visit 2.
- Difference in plasma BNP from Visit 1 to Visit 2
- Difference in plasma carnitine concentration from Visit 1 to Visit 2.
- Correlation of plasma carnitine concentration with TMAO concentration.
- Difference in plasma acylcarnitines from Visit 1 to Visit 2.
- Difference in lipid metabolites from Visit 1 to Visit 2.
- Change in plasma carnitine from Visit 2 to Visit 3.
- Difference in RV function from Visit 2 to Visit 4.
- Difference in plasma acylcarnitine profile from Visit 2 to Visit 4.
- Difference in lipid metabolites from Visit 2 to Visit 4.
- Correlation of change in plasma carnitine with change in Functional class.
- Correlation of change in plasma carnitine with change in six minute walk distance.
- Correlation of change in plasma carnitine with change in BNP.
- Correlation of change in plasma carnitine concentration with TMAO concentration
- Correlation of change in plasma carnitine with change in markers of RV function including TAPSE and RV fractional area change.
- Markers of tolerability including presence of side effects, adverse events and serious adverse events.

- Pill counts at Visit 4 for adherence
- 5.2 Secondary Outcome Measures

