5.2.5 Transthoracic Echocardiographic Measures

We will assess RV free wall longitudinal strain and other parameters as secondary endpoints via transthoracic echocardiography. The ultimate determinant of outcome in subjects with PAH is right ventricular function, so we have focused on metrics, which are predictors of survival in PAH, including RV strain and qualitative RV function. The following metrics will be obtained: 1) tricuspid annular plane systolic excursion (TAPSE); 2) RV & LV ejection fraction⁵¹; 3) RV fractional area change; 4) tricuspid annular velocity (S'); 5) tricuspid regurgitant (TR) velocity; 6) RV systolic pressure (estimated from the equation: RV systolic pressure = 4(maximum TR velocity)⁶¹ + right atrial pressure); 7) right atrial pressure⁵⁹; 8) RV & LV diastolic function⁵³; 9) RV free wall longitudinal strain^{54,60}. All measurements will be performed according to the American Society of Echocardiography guidelines^{51,53,59}.

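### The plan does not mask echocardiographic measurement to visit, so in this single-arm before/after comparison any reader expectation would pass into the reported RV change

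*Combined protocol and SAP*

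**What the plan says.** The study has one arm. Section 2.1 states that "All eligible participants will be given carnitine supplements for 2 weeks", and Section 3.3 names a commercial product with no placebo: "The VUMC Pharmacy for Research will supply Nature's Bounty L-Carnitine 500mg caplets to be taken by mouth".

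The Protocol Summary (Study Observations) gives the echo timing: "Subjects will have a transthoracic echocardiogram at Visit 2 and Visit 4". The schedule in Section 4.3 agrees. Section 4.2.4 lists the Visit 2 echo ahead of dosing, so the first scan precedes the course and the second follows it.

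Two secondary endpoints in Section 5.1 use these scans. The first is the before/after comparison, listed as "Difference in RV function from Visit 2 to Visit 4". The second relates the same readings to each patient's carnitine response and is listed as "Correlation of change in plasma carnitine with change in markers of RV function including TAPSE and RV fractional area change".

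On how the values are produced, Sections 4.2.4 and 4.2.7 say that "An experienced research sonographer will perform the transthoracic echocardiography". Section 5.2.5 lists nine numbered metrics, among them TAPSE, fractional area change and RV free wall strain, and adds that "All measurements will be performed according to the American Society of Echocardiography guidelines". Its rationale also describes a focus on predictors of survival "including RV strain and qualitative RV function".

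The plan does not say who measures the images, what that person knows, or in what order studies are read. The word masking occurs only in the heading of Section 6.6, and the text beneath it covers toxicity and serious adverse events. Section 8 on quality control deals with training and data monitoring.

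**The concern.** Fractional area change and strain depend on the reader's choice of frame and border. A reader who knows which scan followed supplementation can shift these choices slightly without meaning to. In a randomised trial with masked arms, such a shift would fall on both arms and largely cancel. Here nothing can cancel it, because the estimate is simply the after value minus the before value.

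Section 6.2 applies a significance test to continuous endpoints and reports the mean change with a 95% confidence interval as the size of the treatment effect. A reading shift would be reported under that label. What is at stake is how two secondary endpoints are interpreted. The primary result is not at stake.

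**Working it through.** **1. The plan's own figure.** The only power statement (Section 6.1) is for plasma carnitine. The SD of differences is 11.1 × √(2 × (1 − 0.7)) = 8.598, stated as 8.6. The change is 0.22 × 38.6 = 8.49, stated as 8.5. For a paired t-test with n = 10 and two-sided alpha 0.05, df = 9 and the noncentrality is (8.5/8.6) × √10. Power is 79.4%, which agrees with the stated 80%. At effect size 1 it is 80.3%. No stated figure is wrong, and none is given for RV measures.

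**2. How a reading shift enters.** If d is the true Visit 2 to Visit 4 change and b a systematic shift in the Visit 4 reading relative to Visit 2, the expected observed change is d + b. With one arm, no contrast removes b.

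**3. What a shift would do to the test.** The documents give no SD, repeatability or reader error for any RV measure, so b is assumed and expressed in SDs of the within-patient difference. With d = 0 the noncentrality is b × √10. For example, 0.25 × 3.162 = 0.791 and 0.5 × 3.162 = 1.581. Rejection probabilities come from the noncentral t distribution with df = 9:

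| Assumed shift (SD) | Two-sided rejection | Significant in the direction of the shift |
|---|---|---|
| 0 | 5.0% | 2.5% |
| 0.1 | 5.9% | 4.7% |
| 0.2 | 8.8% | 8.2% |
| 0.25 | 10.9% | 10.6% |
| 0.3 | 13.6% | 13.4% |
| 0.5 | 29.3% | 29.3% |

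For scale, an observed mean change of about 0.72 SD reaches p < 0.05 at n = 10.

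**4. Test assumed.** Section 6.2 allows a paired t-test or a Wilcoxon test and refers to change from Visit 1, where no echo is done. The table uses the paired t-test on the Visit 2 to Visit 4 contrast that Section 5.1 defines.

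**5. The correlation endpoint.** A shift that is equal in all patients leaves a correlation coefficient unchanged. That endpoint would be distorted only if the shift followed the patient's carnitine response, which requires the reader to know or guess it. This is why carnitine results should be withheld as well as visit labels.

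**The case against.** The strongest reply is that this is a 10-patient proof-of-concept study whose primary endpoint is a plasma assay that no echo reader can influence. RV function is absent from the stated primary and secondary objectives, and these two endpoints are among 20 secondary items in Section 5.1, with no power calculation or success criterion. Measurements must follow published guidelines, and BNP, which the plan regards as reflecting RV function, is drawn at all four visits and does not depend on image reading. All of this stands and limits the weight of the point. It does not answer it, because guidelines standardise technique without concealing the visit, and the plan still tests the change and reports it as a treatment effect.

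A reader might infer more than the documents support:
- **That RV change would justify the follow-on study.** No section says so. The opening statement of aims gives plasma carnitine as the primary endpoint and mentions better RV function only as a possibility.
- **That a qualitative RV grade is an endpoint.** Qualitative function appears once, in the rationale of Section 5.2.5. It is not among the nine numbered metrics, and no grading scale is given.
- **That the reader is known to be unmasked.** The plan is silent. The sentence about the sonographer concerns acquisition, and no reader is named.
- **That bias is present at the sizes shown.** The table shows how a t-test responds to a shift. It is not evidence of one.
- **That masked reading would make the change attributable to carnitine.** Acquisition effects, time trends and regression to the mean would all remain.

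**Conclusion.** The point holds as an omission that is worth correcting. Reader-dependent RV measures feed two secondary endpoints, visit reveals treatment status, and the plan does not mask measurement to visit. Any systematic expectation effect would therefore enter the Visit 2 to Visit 4 change undiluted. Under assumed shifts of 0.25 and 0.5 SD with no true change, a nominal 5% test rejects in 10.9% and 29.3% of cases. These rates rest on the assumed shifts, a paired t-test and 10 complete pairs. The documents do not allow the actual size to be estimated.

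The primary endpoint, the sample size and the stated power are unaffected. With or without masked reading, an RV change in this design is exploratory.

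**What to change.** In Section 5.2.5, state that whoever measures the echocardiograms for research reads all Visit 2 and Visit 4 studies offline after Visit 4, with dates and visit labels removed, order randomised within patient, and no access to carnitine results. With 10 patients and two scans each, this is up to 20 studies. Also state that RV change is exploratory, because masked reading does not deal with acquisition effects, time trends or regression to the mean.

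The cost is the de-labelling work and later research reads. No patient, visit or procedure is added, and N and power do not change. No extra reader is needed if the person who would measure the images anyway does the masked reads. Because the plan names no reader, the sponsor should confirm this. If the scanning sonographer also measures, recall of individual scans could weaken the masking, and the section should acknowledge it.

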4.3 Study Schedule of Endpoints and Procedures

The table below summarizes the study endpoint assessments and procedures.

	Phone Call	Visit 1	Phone Call	Visit 2	Visit 3	Phone Call	Visit 4
		Observational Period		Supplement Period			
Day	-3	0	80	84 (+/- 5 days)	85	92 (+/- 5 days)	99 (+/- 5 days)
Week	-1	0	11	12	12	13	14
Informed Consent	х						
History and Physical							
Vital Signs		Х		Х	Х		х
Medical History		Х		Х			х
Medication review		Х		Х		х	х
Physical Exam		Х		Х			х
Functional Class		Х		Х			х
Symptom Assessment		Х		Х	Х	х	х
Testing							
Phlebotomy							
CBC		Х		Х	Х		х
СМР		Х		Х	Х		х
BNP		Х		Х	Х		х
Carnitine assay		Х		Х	Х		х
Lipid metabolites		Х		Х	Х		х
Carnitine		Х		Х	Х		х
Acylcarnitine		Х		Х	Х		х
6MWTD		х		х			х
Echo				х			Х

Urine Pregnancy Test				х			
Study Procedures							
ASA-24 Dietary Assessment	x	x	x	x			
Carnitine supplement (3g/day x 2 weeks)				x	x	х	
Adverse events				х	х	х	х
Supplement compliance					x	х	x

 Table 1. Study Procedures

5 Assessments of Efficacy and Outcome Measures

5.1 Assessments of Efficacy

Primary Endpoint: Difference in plasma carnitine concentration from Visit 1 to Visit 4.

Secondary Endpoints:

- Quantify the prevalence of carnitine supplement use
- Measure oral ingestion of carnitine in PAH patients.
- Difference in six-minute walk test from Visit 1 to Visit 2.
- Difference in functional class from Visit 1 to Visit 2.
- Difference in plasma BNP from Visit 1 to Visit 2
- Difference in plasma carnitine concentration from Visit 1 to Visit 2.
- Correlation of plasma carnitine concentration with TMAO concentration.
- Difference in plasma acylcarnitines from Visit 1 to Visit 2.
- Difference in lipid metabolites from Visit 1 to Visit 2.
- Change in plasma carnitine from Visit 2 to Visit 3.
- Difference in RV function from Visit 2 to Visit 4.
- Difference in plasma acylcarnitine profile from Visit 2 to Visit 4.
- Difference in lipid metabolites from Visit 2 to Visit 4.
- Correlation of change in plasma carnitine with change in Functional class.
- Correlation of change in plasma carnitine with change in six minute walk distance.
- Correlation of change in plasma carnitine with change in BNP.
- Correlation of change in plasma carnitine concentration with TMAO concentration
- Correlation of change in plasma carnitine with change in markers of RV function including TAPSE and RV fractional area change.
- Markers of tolerability including presence of side effects, adverse events and serious adverse events.

- Pill counts at Visit 4 for adherence
- 5.2 Secondary Outcome Measures

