Our overarching hypothesis is that in human PAH, RV function can be improved by augmenting carnitine substrate availability to improve outcomes. In preparation for a future mechanistic study, we now propose to test the specific hypothesis that carnitine consumption is not reduced in PAH, that plasma carnitine levels are stable over time in PAH and that carnitine supplementation in PAH can increase plasma carnitine and thereby delivery of carnitine to the RV and possibly improve RV function. We propose three aims in humans to test this mechanistic hypothesis, 1) Measure the oral consumption of carnitine in human PAH. This aim will use food diaries and carnitine supplement use questionnaires in PAH patients to test the hypothesis that carnitine supplementation is uncommon in PAH and food consumption is adequate. Aim 2) Measure the stability over time in plasma carnitine levels in PAH patients. This aim will test the hypothesis that plasma carnitine is not affected by disease severity and is stable over time in PAH patients. We will measure plasma carnitine concentration and markers of fatty acid oxidation at Visit 1 and Visit 2. 3) Perform a mechanistic pilot study using carnitine supplementation to enhance circulating carnitine in PAH. This small pilot study will test the hypothesis that carnitine supplementation increases plasma carnitine (primary endpoint) and will test for physiologic effects using six minute walk testing, echocardiography and plasma markers of lipid metabolism.

Protocol Summary

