6.2 Statistical Analysis

The primary endpoint and other continuous endpoints will be summarized using the mean, standard deviation, the median, and interquartile range. We will use either the paired t-test or the Wilcoxon-signed rank test to assess the change from Visit 1 on these endpoints. Estimate of mean change along with its 95% confidence interval will be reported to quantify the treatment effect. To assess tolerability of carnitine, we will closely monitor any adverse events. For these binary events, proportion of subjects who experience the event will be calculated along with its 95% confidence interval. We will use the open-source statistical package R⁵⁷ for analyses.

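### The primary endpoint measures the supplement effect from Visit 1, about 84 untreated days before supplementation starts, so any mean carnitine change in that period counts as effect or hides it

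*Combined protocol and SAP*

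**What the plan says.** Section 5.1 sets the "Primary Endpoint: Difference in plasma carnitine concentration from Visit 1 to Visit 4". Section 6.2, repeated under Data Analysis in the Protocol Summary, says a paired t-test or signed-rank test will "assess the change from Visit 1 on these endpoints", meaning the primary and the other continuous endpoints, and that the mean change with its 95% interval "will be reported to quantify the treatment effect".

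Section 4.2 and Table 1 place Visit 1 at Day 0, Visit 2 at Day 84 (±5), Visit 3 at Day 85 and Visit 4 at Day 99 (±5). Table 1 labels the stretch that begins at Visit 1 as observational. On the start of treatment, section 3.3 says "A 14-19-day supply of Carnitine supplements will be provided to the subject at Visit 2"; section 4.2.4 and Table 1 also place the supplement at Visit 2, whereas section 4.2.5 hands out the two-week supply at Visit 3. Every participant is supplemented.

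Other endpoints in section 5.1 use a different reference visit, for example "Difference in RV function from Visit 2 to Visit 4"; acylcarnitines and lipid metabolites also run from Visit 2 to Visit 4. The change-on-change correlations, such as "Correlation of change in plasma carnitine with change in BNP", name no visits. Carnitine from Visit 1 to Visit 2 and from Visit 2 to Visit 3 are secondary endpoints. Section 5.1 lists no Visit 2 to Visit 4 change in carnitine.

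**The concern.** In a single-arm before-and-after trial, the choice of baseline defines the effect. The primary aim concerns supplementation, which lasts about two weeks, but the primary contrast covers about fourteen, of which roughly 84 of 99 days are untreated. No control arm can remove a change in the untreated period, and no section corrects the primary estimate for it.

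The contrast is unbiased only if mean carnitine does not move between Visits 1 and 2. Aim 2 in the introduction treats this as an open question: the hypothesis that "plasma carnitine is not affected by disease severity and is stable over time in PAH patients" is to be tested on those same two visits. The primary analysis thus assumes the answer to another aim.

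The reference-visit rules also disagree:

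- Section 6.2's Visit 1 rule conflicts with the Visit 2 to Visit 4 endpoints in section 5.1. It cannot be computed at all for RV function, because no echocardiogram is done at Visit 1.
- Section 6.1 sizes the trial on a rise after two weeks of treatment but starts that rise from the Visit 1 mean.
- The Protocol Summary gives Visit 3 to Visit 4 for acylcarnitines and lipid metabolites, where section 5.1 gives Visit 2 to Visit 4. Because the sections differ on when supplementation begins, it is unclear whether the Visit 3 sample is untreated.

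**Working it through.** **Inputs (section 6.1).** n = 10; mean 38.6 uM; SD 11.1; within-subject correlation 0.7; target change 8.5 uM; two-sided 5% paired t-test. Power below is exact, from the noncentral t distribution with 9 degrees of freedom and noncentrality (mean difference / SD of differences) × √10.

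**Step 1. Reproduce the plan's figure.** SD of differences = 11.1 × √(2 × (1 − 0.7)) = 8.60. Power for 8.5 uM is 79.4%, which agrees with the stated 80%. The standard error is 8.6/√10 = 2.72 uM.

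**Step 2. What the primary contrast estimates.** Expected (Visit 4 − Visit 1) = supplement effect + mean change from Visit 1 to Visit 2. The bias equals the mean drift. Individual fluctuation around a stable mean adds variance but no bias.

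**Step 3. Size.** The documents give no drift figure, so 5%, 10% and 15% of 38.6 uM are assumptions.

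| Assumed drift | uM | False-positive rate if it is a rise and the supplement does nothing (nominal 5%) | Power for a true 8.5 uM if it is a fall (79% without drift) |
|---|---|---|---|
| 5% | 1.93 | 9.8% | 58% (net 6.57 uM) |
| 10% | 3.86 | 24.6% | 33% (net 4.64 uM) |
| 15% | 5.79 | 47.7% | 15% (net 2.71 uM) |

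**Step 4. A larger true effect.** Section 1.5 cites total carnitine about 25 umol/L above control in healthy men. If the rise here were 25 uM (an assumption), power after a 10% fall would stay above 99.9%, but the estimate would still be off by 3.86 uM, which is 3.86/25 = 15%.

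**Step 5. Can the secondary Visit 1 to Visit 2 comparison rule drift out?** Taking the same SD of 8.6, its 95% half-width is 2.262 × 2.72 = 6.15 uM, which is 16% of 38.6 and 72% of 8.5. A true 10% drift would be detected about 25% of the time.

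**Step 6. Power with a Visit 2 baseline.** The plan does not say what interval its correlation of 0.7 refers to. Correlations other than 0.7 are assumptions.

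| Correlation | SD of differences | Power for 8.5 uM |
|---|---|---|
| 0.5 | 11.10 | 58% |
| 0.6 | 9.93 | 67% |
| 0.7 (plan) | 8.60 | 79% |
| 0.8 | 7.02 | 92% |

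**Step 7. Averaging Visits 1 and 2 as baseline.** With equal correlations of 0.7, SD = 11.1 × √(1.5 × 0.3) = 7.45. Without drift, power for 8.5 uM is 89%. Half of any drift remains: a 10% drift leaves 1.93 uM and a false-positive rate of 11.4%.

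**The case against.** The best case for the plan has four parts.

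First, the harm is conditional. No document shows drift. Patients are not selected on their carnitine level, so regression to the mean is not built in. They need a stable PAH regimen, samples are fasting and diet is recorded. The false-positive rates also require that oral carnitine does nothing to plasma carnitine, which section 1.5 makes unlikely. This stands as a limit on how likely the larger distortions are. It does not make the estimate right: the plan promises an effect size with a confidence interval, and drift shifts that even when significance is secure. Section 1.4 says intake varies with diet, and neither diet nor supplement use is restricted between Visits 1 and 2.

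Second, the Protocol Summary has a line pairing Visit 1 to Visit 2 with Visit 3 to Visit 4 for carnitine, just after a primary-endpoint label with no text under it. It may be the summary's primary endpoint, displaced in the extracted text. If so, the summary already separates the untreated period. It would then conflict with section 5.1, not correct it, and it would start from a visit whose treatment status is unclear.

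Third, the averaged baseline in step 7 gives more power, 89% against 79%. That is true only if there is no drift, which is the point in doubt.

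Fourth, for six-minute walk, functional class and BNP, section 5.1 lists only Visit 1 to Visit 2 differences, so a Visit 2 to Visit 4 change is a newly defined contrast. That is fair, although the planned correlations already need a defined change for each, and the data are scheduled.

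**Conclusion.** The point holds and should be corrected before analysis. As written, the primary contrast estimates the supplement effect plus any mean change over about 84 untreated days, and nothing in the plan separates the two. If mean carnitine is stable, the bias is zero. For an assumed 10% drift it is 3.86 uM, or 45% of the 8.5 uM target (3.86/8.5).

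These figures rest on the plan's n and SD of differences, on that SD applying equally to each pair of visits, and on drift sizes that are illustrations. The plan's power calculation is not in error; the reference visit is. A Visit 2 sample is an untreated baseline whether the supplement starts at Visit 2 or Visit 3, provided it is drawn before the first caplet.

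**What to change.** 1. **Protocol Summary, 5.1 and 6.1.** State the primary endpoint as: *change in plasma carnitine concentration from the fasting Visit 2 sample, drawn before the first caplet, to Visit 4*. In 6.1, refer to the Visit 2 mean in place of the Visit 1 mean.
2. **6.2 and Protocol Summary.** State: *for supplement-effect endpoints (carnitine, acylcarnitines, lipid metabolites, BNP, six-minute walk distance, functional class, RV function), change is measured from Visit 2 to Visit 4; the Visit 1 to Visit 2 change is reported for the stability aim only*.
3. **Correlations of change.** Name Visit 2 to Visit 4 for both variables in each one.
4. **Consistency.** Bring the Protocol Summary's Visit 3 to Visit 4 lines, including the one for carnitine, into line with 5.1. Reconcile 3.3, 4.2.4 and Table 1 with 4.2.5 on when the supplement is first given.
5. **Sensitivity analysis.** The mean of Visits 1 and 2 may be used as an alternative baseline here only.

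The cost is a change of text. The Visit 2 fasting blood sample, walk test, functional class and echocardiogram are already scheduled, so no visit, sample or patient is added.
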